### 3.8 Rationale to Changes to Study; 5/5/2023

Two changes to eligibility will be made. First, eligibility will be broadened to include stage 2 skin GVHD (Grade I), or isolated upper GI GVHD to better reflect current treatment practices. These patients were initially excluded because topical therapy alone is a treatment option. However, we analyzed treatment practices for 113 pediatric transplant recipients from 2019-2023 who developed GVHD. Systemic steroid treatment was initiated for 16/28 (57%) of patients who presented with skin stage 2 GVHD and for 10/14 (71%) of patients who presented with isolated upper GI GVHD. The subset with Ann Arbor 1 GVHD had a similar response rate to steroids (75%) as the overall Minnesota Standard risk/AA1 population, are appropriate to include in this study, and their inclusion will help meet accrual goals in a timely manner.

Second, we will remove exclusion criteria for organ function and performance score (with the exception that patients requiring mechanical ventilation and/or cardiac pressors will remain excluded). This change is being made because GVHD occurs in patients with a broad range of morbidities, and patients with organ dysfunction may benefit from reduction in steroid exposure. Inclusion of patients with serious comorbidities will improve the generalizability of the approach and given that this is a treatment de-escalation approach is unlikely to increase risk to subjects.

### 3.9 Summary of Study Rationale

Acute graft-versus-host disease (GVHD) that requires systemic treatment continues to be a problem for children who undergo allogeneic hematopoietic cell transplant with a cumulative incidence of 35%. High dose systemic steroid therapy for weeks to months remains the standard of care even though the majority of pediatric GVHD is low risk. The status quo persists for two reasons. First, initial GVHD severity does not reliably predict treatment response. Second, physicians are uncertain whether early treatment responses will be durable and delay steroid tapers. Thus, steroid-related short and long-term complications are common, even though most children are **over-treated** for steroid responsive GVHD. The aggressive steroid tapers needed to substantially reduce steroid exposure have not been successful in adults due to a fear of treatment failure, the absence of a validated steroid taper algorithm, and an uncertain risk/benefit ratio. To the best of our knowledge, there have been no attempts to study aggressive steroid tapers in children with GVHD.

MAGIC developed and validated a biomarker risk stratification system that identifies the large population of children whose GVHD is **low-risk**. A real-time monitoring system that incorporates two additional clinical and biomarker response measurements over two weeks identifies an even lower risk group that comprises 40% of all pediatric GVHD cases and who are candidates for the

rapid tapers needed to reduce steroid complications. This trial will be the first ever aimed at decreasing the toxicity of GVHD treatment by **personalizing steroid dosing** based on serial assessments of clinical and biomarker responses. If successful, this trial has the potential to change the way acute GVHD is treated in children. This study also will improve the knowledge gap regarding the illness experience in children with acute GVHD by analysis of patient reported outcomes.

## **4.0 STUDY OBJECTIVES**

### **4.1 Primary Objectives**

- 4.1.1 To improve the proportion of pediatric patients whose low-risk GVHD is successfully treated with low cumulative doses of steroids from 14% to 42%.

### **4.2 Secondary Objectives**

Secondary and exploratory objectives will be assessed in all study subjects and in the ultra-low risk patient subset

- 4.2.1 To determine the overall response rate at day 28 of treatment
- 4.2.2 To calculate the duration of response
- 4.2.3 To calculate the incidence of serious infections (overall, viral, bacterial, fungal, parasitic) by day 90 of treatment
- 4.2.4 To determine the cumulative steroid exposure through days 28 and 90 of treatment
- 4.2.5 To determine the incidence of 1 year NRM, relapse, overall survival, and chronic GVHD
- 4.2.6 To determine the incidence of steroid-refractory GVHD in patients by day 90 of treatment

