### 3.4 GVHD Biomarker Algorithm Identifies Patients with Low Risk GVHD

MAGIC has validated a biomarker-based risk stratification system that is more accurate than clinical symptoms at classifying GVHD severity. The MAGIC algorithm probability (MAP) define the Ann Arbor (AA) risk scores (1, 2 or 3) that identify patients at high risk for treatment failure as well as patients who respond well to steroids and would benefit from reductions in treatment. The MAP reflects the extent of GI crypt damage as measured by serum concentrations of ST2 and REG3a. The presence of GI crypt damage portends a worse outcome, even when GI symptoms are minimal or absent, while the absence of GI crypt damage predicts response to steroid treatment, even when GI symptoms are present. The MAP has also been validated as a response biomarker and more accurately predicts survival than clinical response.

Recently we validated the MAGIC algorithm at start of steroid treatment for GVHD in 194 children (median age 12y, range 0.3-21y). Ann Arbor 1 GVHD (65% of patients) represents the best risk group with 2% NRM and each increase in Ann Arbor score represented a highly significantly increase in risk for NRM [Figure 2]. An analysis restricted to children <12y yielded similarly significant results. The area under the curve (AUC) for NRM was significantly better for Ann Arbor scores than clinical severity (0.84 vs 0.63, p=0.007). Ann Arbor scores were predictive of outcomes regardless of onset GVHD severity and within subgroups such as graft type (marrow, peripheral blood, or cord blood), use of anti-thymocyte globulin during conditioning, or diagnosis.

[figure not shown]

Figure 2. NRM in 194 pediatric patients from start of steroid treatment by Ann Arbor score.

Further analyses demonstrated that the combination of favorable clinical features (Minnesota standard risk) and biomarkers Ann Arbor 1 score defines a **low risk** population with a good overall response rate (ORR) to steroids (79%), but the risk posed by a 20% treatment failure rate is a barrier to the rapid tapers likely needed to reduce steroid toxicities.

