### 3.5 Serial Monitoring Identifies Patients with Ultra-Low Risk GVHD

Given that the MAP can also act as a monitoring biomarker, we used both the clinical response and the MAP during the first two weeks of systemic steroid treatment to analyze 85 pediatric patients with Minnesota standard risk/AA1 GVHD. MAPs were categorized as high or low using the validated 0.29 threshold. Changes in clinical severity were scored as either response, stable, or progression. Patients who responded by the end of week one and maintained both clinical response and a low MAP at week two (48% of patients), experienced 95% day 28 ORR. Importantly, serial monitoring demonstrated that **slow** clinical responders (17% of patients) have equally good outcomes with a 100% ORR; these patients have stable disease at week one, a response at week two and a low MAP at all three assessments. The remaining patients (35%) either lacked a treatment response or had an increase in their MAP above 0.29. Taken together, serial monitoring identifies 65% of patients with Minnesota standard risk/AA1 GVHD as an **ultra-low risk** group with higher response rates (96% vs 47%, p<0.001) than other patients. Furthermore, GVHD flares that required an increase in treatment occurred in only 5% of patients with ultra-low risk GVHD. Thus, these patients are excellent candidates for a GVHD treatment strategy that minimizes steroid exposure.

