### **14.3 Data Analysis Plans**

The primary endpoint is the proportion of patients who (1) achieve CR, VGPR, or PR by day 28 of treatment without additional immunosuppressive therapy and (2) whose cumulative prednisone exposure is  $\leq 13.5$  mg/kg. The proportion of patients who are successfully treated with  $\leq 13.5$  mg/kg cumulative prednisone dose will be compared to the historical control rate of 14% using a Chi-squared test.

All study patients will be analyzed and when appropriate, subset analyses by ultra-low risk and other patients will be performed. We expect 33 ultra-low risk patients and 17 other patients out of our sample size of 50 study patients, which will be sufficient for subset analyses.

Secondary outcomes such as the overall response rate, duration of response, cumulative incidence of steroid-refractory GVHD, incidence of serious infections (viral, bacterial, fungal, and parasite), cumulative steroid exposure at day 28 and day 90, overall survival at 6 and 12 months, cumulative incidence of NRM at 6 and 12 months, relapse rate at 6 and 12 months, and cumulative incidence of chronic GVHD requiring systemic steroid treatment by one year will be estimated and compared to historical controls.

Continuous variables will be summarized using standard summary statistics such as number of observations (n), mean, standard deviation (SD), minimum and maximum values, median, and 1st and 3rd quartiles. Categorical variables will be summarized in frequency tables as counts and percentages.

Cumulative incidence of non-relapse mortality will be estimated by Gray's method and relapse will be considered as a competing risk. Disease free and overall survival, defined as the time from the transplantation to death or to last follow-up if alive, will be estimated by the method of Kaplan-Meier and the probability curves and 95% confidence intervals will be provided based on the method of Brookmeyer and Crowley.

The exploratory endpoints of linear growth velocity and patient reported outcomes as per Appendix B will be described for patients whose cumulative steroid exposure is  $\leq 13.5$  mg/kg and  $> 13.5$  mg/kg. Linear growth velocity will be expressed as a standard deviation score of the sex- and age-specific mean.

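### Ultra-low-risk status is settled only at week 2, but subset event outcomes mostly run from earlier origins with no landmark, so the contrast with other patients is partly produced by the grouping rule

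*Combined protocol and SAP*

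**What the plan says.** Section 3.5 gives two routes to ultra-low-risk status, both using information gathered after treatment starts. Early responders (48% of the historical low-risk children) responded by week 1 and "maintained both clinical response and a low MAP at week two". Slow responders (17%) are described thus: "these patients have stable disease at week one, a response at week two and a low MAP at all three assessments". This definition stands only in the background section; 9.1 and 14.3 do not restate it.

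Section 4.2 opens with "Secondary and exploratory objectives will be assessed in all study subjects and in the ultra-low risk patient subset". Section 14.3 says that, when appropriate, "subset analyses by ultra-low risk and other patients will be performed", and adds: "We expect 33 ultra-low risk patients and 17 other patients out of our sample size of 50 study patients".

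The outcome clocks are:

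- Steroid-refractory GVHD, day-28 response and cumulative steroid dose: counted by day of treatment (4.2), with day 0 the first day of systemic steroid (5.0).
- Serious infections: treatment start to day 90 (8.2).
- Overall survival: transplantation (14.3).
- Chronic GVHD: enrollment (4.5).
- Duration of response: first response (9.1.5).

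Only duration of response in slow responders starts at about the time status becomes known. No landmark or time-dependent treatment of status is given, and there is no rule for a child who dies, progresses or misses the assessment before week 2. Secondary outcomes are to be compared with historical controls (14.3), without saying that a historical ultra-low-risk subset would be built in the same way.

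**The concern.** To be ultra-low risk, a child must reach week 2 in response with a low MAP. Children with week-1 progression or a high MAP leave the taper schedule (Table 1), as do week-2 non-responders (7.1.7), and under 3.5 they belong to the other group. If events are then counted from day 0, early failures are charged almost wholly to that group, while the ultra-low-risk group is credited with about two weeks in which such failure was close to impossible by construction.

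Steroid-refractory GVHD is the outcome most exposed. One of its two limbs in 9.1.3 is worsening that needs a non-steroid agent, and before week 2 that nearly always puts a child in the other group. The second limb, no response by day 28, overlaps with the week-2 response used for classification. Section 10.6 names refractory GVHD as the main risk of a rapid taper, so a favourable subset rate is likely to be read as evidence about the taper.

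**Working it through.** **1. The plan's own figures reproduce.**

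- Ultra-low-risk share: 48% + 17% = 65%. Of 50 patients, 0.65 × 50 = 32.5 and 0.35 × 50 = 17.5, stated as 33 and 17.
- Historical day-28 response in the subset: (0.48 × 0.95 + 0.17 × 1.00)/0.65 = 96.3%, stated as 96%.
- All low-risk patients: 0.65 × 0.96 + 0.35 × 0.47 = 78.9%, stated as 79% in 3.4.

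**2. How much of each window precedes classification.** 14/28 = 50% of the day-28 window, 14/90 = 16% of the day-90 window, and 14/365 = 4% of one year.

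**3. Steroid-refractory GVHD with no true difference.** Inputs: total rate T = 15% by day 100 (10.6), N = 50, and a 65/35 split. The proportion p with an event before day 14 is not in the documents, so three values are assumed. Patients with an event before day 14 go to the other group; the rest are allocated at random to fill 32.5 and 17.5 places.

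- Risk after day 14 in those still event-free: r = (T − p)/(1 − p). This is the ultra-low-risk rate and also the landmark rate in both groups.
- Other group counted from day 0: [50p + (17.5 − 50p) × r]/17.5.

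Constant hazard: p = 1 − 0.85^(14/100) = 0.0225, so 50p = 1.12 patients. Then r = 0.1275/0.9775 = 13.0%, and the other group shows (1.12 + 16.38 × 0.1304)/17.5 = 18.6%.

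A quarter of events before day 14: p = 0.0375, 50p = 1.875, r = 0.1125/0.9625 = 11.7%; other group (1.875 + 15.625 × 0.1169)/17.5 = 21.1%.

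Half before day 14: p = 0.075, 50p = 3.75, r = 0.075/0.925 = 8.1%; other group (3.75 + 13.75 × 0.0811)/17.5 = 27.8%.

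| Assumed timing | Ultra-low risk, day 0 | Other, day 0 | Ratio | Day-14 landmark, each group |
|---|---|---|---|---|
| Constant hazard | 13.0% | 18.6% | 1.4 | 13.0% |
| 25% before day 14 | 11.7% | 21.1% | 1.8 | 11.7% |
| 50% before day 14 | 8.1% | 27.8% | 3.4 | 8.1% |

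**4. Non-relapse mortality.** Section 3.4 gives 2% for Ann Arbor 1 children; a six-month (180-day) horizon is assumed. Under a constant hazard, 50 × [1 − 0.98^(14/180)] = 0.08 deaths are expected before day 14. If half of all deaths came that early, the figure would be 0.5 × 0.02 × 50 = 0.5 of a death.

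**5. Infections.** A serious infection before day 14 does not by itself bar a child from ultra-low-risk status, so those days are not immortal time. Any bias comes from selecting on early response.

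**6. Day-28 response.** Membership requires response at week 2, so the historical contrast ("higher response rates (96% vs 47%, p<0.001) than other patients") already contains the classification criterion, and the trial's subset rate will too.

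**The case against.** The strongest reply is that nothing decisive rests on this contrast. The subset analyses are conditional on being appropriate, and no test of ultra-low-risk against other patients is named. The grouping is prognostic, so different outcomes are expected. The primary endpoint (4.4) uses all low-risk patients, and the stopping rule (10.6) monitors the whole study population. Section 14.2 bases the phase III decision on listed endpoints without mentioning the subset. Section 3.5 describes a historical subset formed by the same week-2 rule, so a like-for-like comparison is available. All of this stands and limits the point to descriptive results. It does not make day-0 subset rates interpretable, and 14.3 does not commit to building the comparator in the same way.

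The size can also be questioned. No response by day 28 cannot be established by day 14, and steroid escalation does not count as refractory (9.1.3), so few events may fall early. Under a constant hazard the spurious gap is 18.6 − 13.0 = 5.6 percentage points, against a standard error of about 11 points: √(0.130 × 0.870/32.5 + 0.186 × 0.814/17.5) = 0.110. That is fair. The bias nevertheless runs in one direction, whereas sampling error does not.

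Section 9.1.1 defines weekly treatment response without regard to new lines of therapy. A child given second-line treatment who is in response at the assessments is therefore not clearly excluded from the subset. Hence early failures fall almost entirely, rather than entirely, into the other group.

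A reader might infer a larger effect, for instance 10% versus 36% if 5 of 17 other patients were refractory before day 14 and everyone else had a 10% risk: (5 + 0.10 × 12)/17 = 36%. That scenario implies (5 + 1.2 + 3.3)/50 = 19% refractory overall, above the 15% in 10.6, so the documents do not support it.

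**Conclusion.** The concern holds for two results: the ultra-low-risk versus other contrast for steroid-refractory GVHD, and the subset's day-28 response. With no true difference and 15% refractory by day 100, counting from day 0 produces an apparent ratio of 1.4 to 3.4. A day-14 landmark gives 1.0. These figures rest on assumed event timing and on random allocation of patients who are event-free at day 14; they are illustrations, not estimates.

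A reader might go further and infer that every subset outcome is counted from day 0, that survival is materially inflated, or that the trial's safety conclusion is biased. The documents support none of these. Overall survival, chronic GVHD and duration of response have other origins; hardly any deaths are expected before day 14; and the formal safety monitoring covers all patients. Nor would a landmark make the two groups comparable: it removes the immortal time but leaves the selection on early response.

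**What to change.** In 14.3:

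- Define ultra-low-risk status operationally, classify each patient at the week-2 visit, and say how a child without that assessment is handled.
- For ultra-low-risk versus other and subset analyses of steroid-refractory GVHD, serious infections, NRM, relapse, overall survival and chronic GVHD, start the clock at that visit among patients alive and free of the event in question.
- Tabulate events before the landmark for the whole cohort.
- Build and landmark any historical ultra-low-risk comparator in the same way.
- Label subset day-28 response as conditional on week-2 response, and the subset contrasts as descriptive.

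Three things should stay as they are. Cumulative steroid exposure should run from day 0, because a restart would discard two weeks of the dose being measured. Duration of response should follow 9.1.5, reported as conditional on week-2 status. All-patient analyses are unchanged.

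Table 2 already schedules staging and a serum sample at day 14, within a window of two days either side, so no new data are needed. The cost is SAP wording, minor programming and slightly fewer events in the subset estimates.

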### **4.3 Exploratory Objectives**

- 4.3.1 To measure quality of life (physical functioning and neuropsychiatric well-being)
- 4.3.2 To calculate linear growth velocity in study patients
- 4.3.3 To calculate the MAP at day 28 of treatment

### **4.4 Primary Endpoint**

Proportion of patients with low-risk GVHD (Minnesota standard risk/Ann Arbor 1) who are in CR, VGPR or PR on day 28 of treatment and whose cumulative prednisone (or other steroid equivalent) exposure during the first four weeks of treatment is  $\leq 13.5$  mg/kg (i.e.,  $<50\%$  of current practice).

### **4.5 Secondary Endpoints**

- 1. Proportion of patients who achieve a treatment response by day 28 of treatment. Treatment responses are defined as complete response (CR), very good partial

response (VGPR), or partial response (PR). For a response to be scored as CR, VGPR, or PR on day 28, the patient must be in response on day 28 and have had no intervening systemic therapy for acute GVHD other than steroids.

2. Proportion of patients who develop serious infections (viral, bacterial, fungal, parasitic as defined in section 9.1.11)
3. Overall survival at 6 and 12 months
4. Cumulative incidence of NRM at 6 and 12 months
5. Relapse rate at 6 and 12 months
6. Cumulative incidence of chronic GVHD requiring systemic steroid treatment by one year from enrollment
7. Cumulative steroid dose at days 28 and 90

#### **4.6 Safety Endpoints**

1. Proportion of patients who develop steroid refractory GVHD defined as GVHD that worsens by at least one stage in at least one target organ **and** requires systemic treatment with an agent other than steroids

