**TABLE 2: TIME AND EVENTS TABLE**

	Screening	Study day 0	Study day 7	Study day 14	Study day 21	Study day 28 	Study day 42	Study day 56	Study day 90	Study day 180	Study day 365	GVHD Flare 
Windows	Newly diagnosed acute GVHD in need of systemic treatment +/- 1 day	Start of prednisone (or equivalent) therapy	+/- 2 days	+/- 2 days	+/- 2 days	+/- 2 day	+/- 3 days	+/- 3 days	+/- 7 days	+/- 14 days	+/- 21 days	+/- 3 days
Eligibility Review	X											
Concomitant Medication Review 	X	X	X	X	X	X	X	X	X			
Steroid Dose Collection	X	Steroid dose will be collected at each study visit during the first 90 days of study and changes occurring outside of the defined timepoints will be captured on an ad hoc form through study day 90										
Adverse Event Evaluations 	X	Adverse events will be reported from study day 0 through day 56. Report serious adverse events as they occur.										
Infections		Infections as defined in sections 9.1.11 will be reported from study day 0 through study day 90										
Serum Chemistry	X											
GVHD Staging 	X	X	X	X	X	X	X	X	X			X
Height and Weight	X					X		X	X	X	X	
Survival, Relapse & Chronic GVHD Status										X	X	
Patient Reported Outcomes		X 				X 			X 	X 		

(PRO) Assessment 												
	CORRELATIVE STUDIES											
5 ml serum 	X		X	X	X	X						X

 The primary endpoint is assessed on day 28 ±2 days

 Concomitant medication review will report **only** immunosuppressants and other drugs administered during the reporting period for GVHD prevention and treatment.

 Serious adverse events are reported as they occur. Other adverse events can be batch reported after day 56 of study.

 GVHD staging will follow the detailed guidelines provided in the MAGIC Acute GVHD Staging Guidance. GVHD staging and treatment should be reported weekly through day 100 post-HCT for patients co-enrolled on the MAGIC natural history study as per the natural history study calendar of events. Steroid dose changes occurring outside of the defined timepoints will be captured on an ad hoc form through study day 90.

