#### **9.1.3 Steroid refractory GVHD**

Steroid refractory GVHD is defined as either an increase by at least one GVHD stage that requires initiation of an additional line of therapy beyond steroids or a lack of response (i.e., NR) by day 28. Escalation of steroid doses during treatment for GVHD are not considered in the definition of steroid refractory GVHD. The resumption or addition of tacrolimus, sirolimus, or cyclosporine will not be considered a new line of treatment.

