## **14.0 STATISTICAL CONSIDERATIONS**

### **14.1 Study Design/Study Endpoints**

This is a phase II, single arm, open-label, multicenter clinical trial to determine the effectiveness of a structured steroid taper, guided by serial biomarker and clinical response in pediatric patients with newly diagnosed, low-risk acute GVHD defined by standard risk clinical criteria (Minnesota) and low risk biomarkers (Ann Arbor 1). The primary study measure is the proportion of low-risk GVHD patients who achieve clinical response (CR, VGPR, or PR) on day 28 after being exposed to low cumulative dose of prednisone ( $\leq 13.5$  mg/kg) or other steroid equivalent during the first 4 weeks of therapy. A single arm phase II design was selected due to the relatively small numbers of allogeneic transplants performed in children.

To further investigate the treatment regimen, we will determine the proportion of patients who achieve a treatment response (CR, VGPR, or PR) by day 28, duration of response, the incidence of steroid refractory GVHD by day 100, and the cumulative steroid dose at days 28 and 90. Secondary endpoints will also include the cumulative incidence of serious infections, patient reported outcomes at days 28, 90, and 180, overall survival at 6 and 12 months, cumulative incidence of NRM at 6 and 12 months, relapse rate, and cumulative incidence of chronic GVHD requiring systemic steroid treatment by one year.

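### Steroid-refractory GVHD, the only listed safety endpoint, is narrower in 4.6 than in 9.1.3 and has two horizons (day 90 and day 100); use one definition and one horizon, and confirm the 15% baseline under them

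*Combined protocol and SAP*

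**What the plan says.** **Definition.** Section 4.6 names one safety endpoint: the proportion of patients with "steroid refractory GVHD defined as GVHD that worsens by at least one stage in at least one target organ" which also "requires systemic treatment with an agent other than steroids". Both conditions must hold, and no time limit is given. Section 9.1.3 gives the same term a wider meaning: "either an increase by at least one GVHD stage that requires initiation of an additional line of therapy beyond steroids or a lack of response", with non-response judged at day 28. It adds: "Escalation of steroid doses during treatment for GVHD are not considered in the definition of steroid refractory GVHD". Sections 9.1.3 and 9.1.7 also say that adding tacrolimus, sirolimus or cyclosporine is not a new line of treatment. Section 4.6 has no such exception.

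**Horizon.** Objective 4.2.6 reads "To determine the incidence of steroid-refractory GVHD in patients by day 90 of treatment", and the synopsis also says day 90. Section 14.1 plans to determine "the incidence of steroid refractory GVHD by day 100". Section 10.2.2 makes the event an SAE up to day 100. Section 10.6 monitors it to day 100 and says that its 15% historical rate uses the 9.1.3 definition by day 100.

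**Use.** Section 14.3 estimates the cumulative incidence and compares it with historical controls, without naming a definition or a horizon. Section 14.2 lists the outcome among those that decide whether to go on to phase III.

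**The concern.** The trial gives children less steroid, so the harm to look for is GVHD that is not controlled. Section 10.6 describes that harm as disease that fails to respond even to higher steroid doses. A child who is still a non-responder at day 28 on steroids alone fits that description, yet 4.6 does not count the child.

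With two definitions and two horizons in force, the team could report either rate after seeing the data. A rate computed under 4.6, or at day 90, would also not be like for like with a historical figure stated under 9.1.3 by day 100. The rate enters the phase III decision, so the choice matters.

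**Working it through.** **1. Who is counted under each definition, at a common horizon**

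| Course | 4.6 | 9.1.3 |
|---|---|---|
| Rises a stage and is given a second-line systemic agent | yes | yes |
| Stable on steroids alone, NR at day 28 | no | yes |
| Second-line agent before day 28 for GVHD that has not worsened (scored NR by 9.1.1) | no | yes |
| Rises a stage, receives only more steroid, NR at day 28 | no | yes |
| Rises a stage, receives only more steroid, in response at day 28 | no | no |

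Every child counted by 4.6 is counted by 9.1.3, and three kinds of child are counted by 9.1.3 only. So the 4.6 count is at most the 9.1.3 count. This assumes that the tacrolimus, sirolimus and cyclosporine exception is read into 4.6. Taken literally, 4.6 could count a child who worsened and had only one of these added, which is one more reason to have a single definition.

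**2. Size of the gap**

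The gap is the share of children who are NR at day 28 but do not meet both 4.6 conditions. The documents give no figure for that share, so the gap cannot be computed.

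**3. The stopping rule as stated**

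I took the 10.6 boundaries and stopped when cumulative cases exceed the boundary, patient by patient up to 50, with exact binomial probabilities.

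| True rate | Plan | Recomputed |
|---|---|---|
| 15% | 0.05 | 0.051 |
| 30% | 0.76 in the text, 0.75 in the table | 0.762 |
| 35% | 0.92 | 0.922 |

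The plan's figures are reproduced.

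**4. Is 15% compatible with 9.1.3?**

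Inputs from 3.5: a response rate of 96% in the 65% with ultra-low risk, and 47% in the other 35%.

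- Response = 0.65 × 0.96 + 0.35 × 0.47 = 0.6240 + 0.1645 = 0.7885, which agrees with the 79% in 3.4.
- Day-28 NR = 1 − 0.7885 = 0.2115, about 21%, or 0.2115 × 50 = 10.6 children.
- The baseline of 15% corresponds to 0.15 × 50 = 7.5 children.

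Under 9.1.3 every day-28 NR is a case, so the rate should be at least about 21% before any later case is added. At a true rate of 21% the same boundaries stop the trial with probability 0.26, against 0.05 at 15%.

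**5. Data after day 90**

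In Table 2, routine staging and review of GVHD medication end at day 90, apart from flare visits. Under 9.1.3 the NR limb closes at day 28, so a new case on days 91 to 100 is a day-28 responder who worsens and starts another line. The flare column calls for staging at the first flare but does not mark medication review. After day 56 the SAE table in 10.4 asks sites for unexpected SAEs that are probably or definitely related, plus deaths. Steroid-refractory GVHD is described in the protocol, so 10.2.3 makes it expected, and the table may not capture it although 10.2.2 calls it an SAE to day 100.

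**The case against.** The strongest reply is that little depends on 4.6, and much of it stands.

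- **Non-responders stay visible.** A reader might infer that they vanish from the results. They do not. Response at day 28 is part of the primary endpoint (4.4) and is the first secondary endpoint (4.5). A second-line systemic agent forces NR there, and 14.2 lists response rate beside steroid-refractory GVHD.
- **Monitoring is anchored.** A reader might infer that the stopping rule would miss cases. Section 10.6 ties its baseline to 9.1.3 and monitors to day 100, so the natural reading is that monitoring uses 9.1.3.
- **Days 91 to 100 are not empty.** Flare visits and the SAE rule in 10.2.2 cover part of them, and the ±7-day window lets the day-90 visit fall as late as day 97. Table 2 also says "Steroid dose will be collected at each study visit during the first 90 days of study", but that limit is irrelevant here because dose escalation is outside the 9.1.3 definition. The remaining gap is capture of new systemic therapy.
- **Day 90 would also be consistent.** Aligning everything on day 90 would remove the horizon conflict too, but would mean changing 10.2.2, 10.6 and 14.1 and restating the 15%.

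What the reply does not remove is that the rate reported as the safety endpoint, and its historical comparison, depend on which section the analyst follows.

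**Conclusion.** The conflict is in the current text and should be resolved. Reporting the endpoint as 4.6 words it gives a count no higher than 9.1.3 would give at the same horizon, provided the same agents count as new therapy. The exposure is limited to the reported safety rate, its comparison with historical controls and its part in the phase III decision. No power or sample-size figure changes.

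Two stronger readings are not supported:

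- **A sized gap.** One could assume that 25%, 50% or 75% of the 21% also meet 4.6 and obtain rates of 5.3%, 10.6% or 15.9%. Those shares are invented. Nor does the standard error of one proportion measure the difference, because both definitions classify the same children.
- **A known bias against the 15%.** If that figure was itself obtained under a narrower definition, 4.6 might be closer to it than 9.1.3 is.

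The mismatch between about 21% and 15% suggests a narrower definition or a different cohort behind the baseline, but does not prove either. The 21% rests on 85 historical patients (3.5), and 10.6 describes the preliminary data as coming from standard steroid doses, so it is not a forecast for this regimen. It is enough to require that the 15% be checked.

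**What to change.** 1. Use one definition and one horizon throughout. The pair consistent with 10.6 is 9.1.3 by day 100: have 4.6 refer to it, change the synopsis and 4.2.6 to day 100, and name both in 14.3.
2. Report two components: worsened and needed second-line therapy, and NR at day 28 only. The first keeps the information that 4.6 was meant to give.
3. Compute the historical comparator under the same definition and horizon.
4. Confirm the 15% baseline under that definition and explain how it fits with a 79% response rate. If it does not hold, restate the operating characteristics in 10.6 at the confirmed rate.
5. If day 100 is kept, record new systemic GVHD therapy through day 100 by chart review, and state in 10.4 that steroid-refractory GVHD is reportable to day 100.

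The cost is protocol wording, one check of the historical data, about ten more days of chart-based reporting, and a reported safety rate that is likely to look less favourable than under 4.6.
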